#### **6.9.2 Local control rate of SRS treated lesions**

As noted above, areas treated with SRS are well known to inflame after therapy. In these cases, the clinical judgment of the radiologist and radiation oncologist will be used to assess the local control of specific lesions. Of note, observation over time may be necessary for definitive assessment of some lesions.

#### **6.9.3 Overall survival**

Overall survival will be measured from the time of initiation of SRS until the time of death.

#### **6.9.4 Toxicity of SRS**

Toxicity of SRS will be graded by NCI CTCAE version 4.

#### **6.9.5 Toxicity of erlotinib post SRS/local ablative therapy**

The toxicity of erlotinib has been well defined in multiple phase III studies. However, two elements are different in this study. First, erlotinib is being used after SRS. While this has been done before in clinical practice, the toxicity has not been systematically assessed. Second, if the therapy is efficacious, patients may spend a longer time on erlotinib and live a longer time, potentially exposing longer-term toxicities that have been masked by previously short PFS and OS.

#### **6.9.6 Veristrat® in EGFR mutated NSCLC**

Veristrat® has been shown to be prognostic in untreated patients as well as predictive of both response and survival in EGFR-TKI treated patients, including patients with EGFR mutation. Although change in Veristrat® result from “good” to “poor” has been demonstrated in patients progressing on an EGFR-TKI, the assay has never been evaluated in the context of a therapy seeking to restore systemic sensitivity to a TKI and a “poor” to “good” transition has never been documented. Exploratory analyses of both the good vs. poor signature and individual peaks will be explored at serial time points.

#### **6.9.7 Responses to subsequent therapies**

It is possible that the study treatment modulates treatment outcomes to subsequent therapies. For example, ablation of clones resistant to erlotinib may also ablate cells that bear resistance to the chemotherapy later chosen. Therefore, to the extent possible, response rate and PFS to subsequent therapy will be recorded on the electronic case report form (eCRF).

#### **6.9.8 Assessment of Disease-Tumor Measurement Based on RECIST 1.1**

Response rate will be assessed for SRS.

Measurable disease will be defined as the presence of at least one measurable lesion that can be accurately measured in at least one dimension with the longest diameter a minimum size of:

- $\geq 10$ mm by CT scan (CT scan slice thickness no greater than 5 mm)
- 10mm caliper measurement by clinical exam (lesions which cannot be accurately measured with calipers should be recorded as non-measurable).
- 20 mm by chest x-ray.

For malignant lymph nodes to be considered pathologically enlarged and measurable, a lymph node must be  $\geq 15$ mm in short axis when assessed by CT scan (CT scan slice thickness recommended to be no greater than 5mm). At baseline and in follow-up, only the short axis will be measured and followed.

All other lesions, including small lesions (longest diameter  $< 10$ mm or pathological lymph nodes with  $\geq 10$  to  $< 15$  mm short axis) as well as truly non-measurable lesions, will be considered non-measurable. Lesions considered truly non-measurable include: leptomeningeal disease; ascites; pleural/pericardial effusion; inflammatory breast disease; lymphangitic involvement of skin or lung, abdominal masses/abdominal organomegaly identified by physical exam that is not measurable by reproducible imaging techniques.

All measurements should be recorded in metric notation, using calipers if clinically assessed. All baseline evaluations should be performed as close as possible to the treatment start and never more than 4 weeks before the beginning of the treatment. The same method of assessment and the same technique should be used to characterize each identified and reported lesion at baseline and during follow-up. Imaging based evaluation should always be done rather than clinical examination unless the lesion(s) being followed cannot be imaged but are assessable by clinical exam. Clinical lesions will only be considered measurable when they are superficial and  $\geq 10$  mm diameter as assessed using calipers (e.g. skin nodules). For the case of skin lesions, documentation by color photography including a ruler to estimate the size of the lesions is recommended.

#### **6.9.9 Baseline Documentation of Target and Non-Target Lesions**

All measurable lesions up to a maximum of 5 lesions total (and a maximum of two lesions per organ) representative of all involved organs should be identified as target lesions and will be recorded and measured at baseline.

Target lesions should be selected on the basis of their size (lesions with the longer diameter), be representative of all involved organs, but in addition should be those that lend themselves to reproducible repeated measurements.

A sum of the diameters (longest for non-nodal lesions, short axis for nodal lesions) for all target lesions will be calculated and reported as the baseline sum diameters. If lymph nodes are to be included in the sum, only the short axis is

added into the sum. The baseline sum diameters will be used as reference to further characterize the objective tumor response of the measurable dimension of the disease.

All other lesions (or sites of disease) including pathological lymph nodes should be identified as non-target lesions and should also be recorded at baseline. Measurements are not required and these lesions should be followed as “present” or “absent”, or in rare cases “unequivocal progression”.

#### **6.9.10 Evaluation of Target Lesions using RECIST 1.1 Criteria**

Complete response (CR)–Disappearance of all target lesions. Any pathological lymph node (LN) (whether target or non-target) must have decreased in short axis to <10mm.

Partial response (PR)–At least a 30% decrease in the sum of the LD of the target lesions taking as reference the baseline sum LD.

Progressive Disease (PD)–At least a 20% increase in the sum of the LD of the target lesions taking as reference the smallest sum LD recorded since the treatment started including baseline if that is the smallest on study. In addition to the relative increase of 20%, the sum must also demonstrate an absolute increase of at least 5mm. The appearance of one or more new lesions also constitutes PD.

Stable disease (SD)–Neither sufficient shrinkage to qualify for PR nor sufficient increase to qualify for PD taking as references the smallest sum LD since the treatment started.

#### **6.9.11 Evaluation of Non-Target Lesions using RECIST 1.1 Criteria**

Complete response (CR)–Disappearance of all non-target lesions and normalization of tumor marker levels. All LN must be non-pathological in size (<10mm short axis).

Non-complete response (non-CR)/non-progression (non-PD)–Persistence of one or more non-target lesion(s) or/and maintenance of tumor marker level above the normal limits.

Progressive disease (PD)–Appearance of one or more new lesions and/or unequivocal progression of existing non-target lesions.

#### **6.9.12 Evaluation of Best Overall Response using RECIST 1.1 Criteria**

The best overall response is the best response recorded from the start of the study treatment until the end of treatment provided the confirmation criteria are met. To be assigned a status of PR or CR, changes in tumor measurements must be confirmed by repeat studies that should be performed > 4 weeks after the criteria for response are first met. If a CR/PR cannot be confirmed the original "response"

should be considered stable disease. The best overall response will be defined according to the following table:

Overall Response First Time Point	Overall Response Subsequent Time Point	BEST Overall Response
CR	CR	CR
CR	PR	SD, PD, or PR 
CR	SD	SD provided minimum criteria for SD duration met, otherwise, PD
CR	PD	SD provided minimum criteria for SD duration met, otherwise, PD
CR	NE 	SD provided minimum criteria for SD duration met, otherwise, NE 
PR	CR	PR
PR	PR	PR
PR	SD	SD
PR	PD	SD provided minimum criteria for SD duration met, otherwise, PD
PR	NE 	SD provided minimum criteria for SD duration met, otherwise, NE 
NE	NE 	NE 

 If a CR is truly met at first time point, then any disease seen at a subsequent time point, even disease meeting PR criteria relative to baseline, makes the disease PD at that point (since disease must have reappeared after CR). Best response would depend on whether minimum duration for SD was met. However, sometimes 'CR' may be claimed when subsequent scans suggest small lesions were likely still present and in fact the patient had PR, not CR at the first time point. Under these circumstances, the original CR should be changed to PR and the best response is PR.

 NE=inevaluable

## 7.0 ADVERSE EVENTS

### 7.1 Definitions

#### 7.1.1 Adverse Event (AE)

An adverse event (AE) is any untoward medical occurrence (e.g., an abnormal laboratory finding, symptom, or disease temporally associated with the use of a drug) in a patient or clinical investigation subject administered a pharmaceutical product and which does not necessarily have a causal relationship with this treatment. An AE can therefore be any unfavorable and unintended sign (including an abnormal laboratory finding), symptom, or disease temporally associated with the use of a medicinal product, whether or not related to the medicinal product.

Hospitalization for elective surgery or routine clinical procedures that are not the result of an AE (e.g., surgical insertion of central line) need not be considered AEs and should not be recorded as an AE. Disease progression should not be recorded as an AE, unless it is attributable by the investigator to the study therapy.

### 7.1.2 Suspected Adverse Reaction (SAR)

A suspected adverse reaction (SAR) is any AE for which there is a *reasonable possibility* that the drug is the cause. *Reasonable possibility* means that there is evidence to suggest a causal relationship between the drug and the AE. A suspected adverse reaction implies a lesser degree of certainty about causality than adverse reaction, which means any adverse event caused by a drug.

Causality assessment to a study drug is a medical judgment made in consideration of the following factors: temporal relationship of the AE to study drug exposure, known mechanism of action or side effect profile of study treatment, other recent or concomitant drug exposures, normal clinical course of the disease under investigation, and any other underlying or concurrent medical conditions. Other factors to consider in considering drug as the cause of the AE:

- Single occurrence of an uncommon event known to be strongly associated with drug exposure (e.g., angioedema, hepatic injury, Stevens-Johnson Syndrome)
- One or more occurrences of an event not commonly associated with drug exposure, but otherwise uncommon in the population (e.g., tendon rupture); often more than once occurrence from one or multiple studies would be needed before the sponsor could determine that there is *reasonable possibility* that the drug caused the event.
- An aggregate analysis of specific events observed in a clinical trial that indicates the events occur more frequently in the drug treatment group than in a concurrent or historical control group

### 7.1.3 Unexpected AE or SAR

An AE or SAR is considered unexpected if the specificity or severity of it is not consistent with the applicable product information (e.g., Investigator's Brochure (IB) for an unapproved investigational product or package insert/summary of product characteristics for an approved product). Unexpected also refers to AEs or SARs that are mentioned in the IB as occurring with a class of drugs or as anticipated from the pharmacological properties of the drug, but are not specifically mentioned as occurring with the particular drug under investigation.

### 7.1.4 Serious AE or SAR

An AE or SAR is considered serious if, in the view of either the investigator or sponsor, it results in any of the following outcomes:

- Death;
- Is life-threatening (places the subject at immediate risk of death from the event as it occurred);
- Requires inpatient hospitalization (>24 hours) or prolongation of existing hospitalization;\*
- Results in congenital anomaly/birth defect;
- Results in a persistent or significant incapacity or substantial disruption of the ability to conduct normal life functions;

- Important medical events that may not result in death, be life-threatening, or require hospitalization may be considered a serious adverse drug experience when, based upon appropriate medical judgment, they may jeopardize the patient or subject and may require medical or surgical intervention to prevent one of the outcomes listed in the definition. For reporting purposes, also consider the occurrences of pregnancy as an event which must be reported as an important medical event.

\*Hospitalization for anticipated or protocol specified procedures such as administration of chemotherapy, central line insertion, metastasis interventional therapy, resection of primary tumor, or elective surgery, will not be considered serious adverse events.

## **7.2 Documentation of non-serious AEs or SARs**

For non-serious AEs or SARs, documentation must begin from day 1 of study treatment and continue until the AE or SAR is resolved or returns to <grade 1 or baseline.

Collected information should be recorded in the Electronic Case Report Forms (eCRF) for that patient. Please include a description of the event, its severity or toxicity grade, onset and resolved dates (if applicable), and the relationship to the study drug. Documentation should occur at least monthly.

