### **2.2 Secondary Objectives**

**2.2.1** To evaluate local control of sites previously progressive on erlotinib following SRS followed by erlotinib

**2.2.2** To estimate OS after locally ablative therapy and erlotinib in EGFR-mutant NSCLC patients who progressed on prior EGFR-TKI therapy

**2.2.3** To characterize the toxicity of SRS

**2.2.4** To characterize the toxicity of erlotinib when preceded by SRS

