## **7.3 SAEs or Serious SARs**

### **7.3.1 Timing**

After informed consent but prior to initiation of study medications, only SAEs caused by a protocol-mandated intervention will be collected (e.g. SAEs related to invasive procedures such as biopsies, medication washout, or no treatment run-in).

For any other experience or condition that meets the definition of an SAE or a serious SAR, recording of the event must begin from day 1 of study treatment and continue through the 30 day follow-up period after treatment is discontinued.

For any other experience or condition that meets the definition of a serious adverse event (SAE) or SAR, recording of the event must begin from day 1 of study treatment and continue through the 30 day follow-up period after treatment is discontinued.

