### 7.3.3 Reporting

#### **FDA Expedited Reporting requirements for studies conducted under an IND:**

If an investigator deems that an event is both a serious SAR AND unexpected, it must also (in addition to Oncore) be recorded on the MedWatch Form 3500A as per 21 CFR 312.32. If the event occurs at an Affiliate site, the MedWatch form should be faxed to the UNCCN Project Manager at [contact] along with supporting documentation defining the event and causality. The MedWatch 3500a form can be accessed at:

<http://www.fda.gov/Safety/MedWatch/HowToReport/DownloadForms/default.htm>.

(Please be sure and access form 3500a, and not form 3500). UNC, as the Sponsor of the study, will make the final determination regarding FDA submission.

UNC study personnel are responsible for informing the Principal Investigator of the SAE, and, if it is also a serious SAR AND unexpected, for forwarding all MedWatch 3500A forms to the FDA in accordance with 21 CFR 312.32 (for drugs under an IND) and 21 CFR 314.80 (for marketed drugs).

The UNCCN Project Manager will also be responsible for informing each Affiliate site of all serious and unexpected SARs via fax as soon as possible.

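### Safety attribution and the affiliate-site alert are framed on the drug, so a serious unexpected event attributed only to SRS or other ablation has no written trigger for prompt notice to the other sites

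*Combined protocol and SAP*

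**What the plan says.** Section 2.2.3 sets the objective "To characterize the toxicity of SRS", and 2.2.4 sets a separate one for erlotinib given after SRS. Sections 1.1 and 4.2 make ablation of the progressing sites part of treatment for every patient.

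The safety rules in section 7 run as follows.

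- **7.1.2 (SAR).** There must be a reasonable possibility "that the drug is the cause", which "means that there is evidence to suggest a causal relationship between the drug and the AE". The assessment itself is introduced with "Causality assessment to a study drug is a medical judgment made in consideration of the following factors".
- **7.1.3 (unexpected).** The comparison is with product information, such as an investigator's brochure or package insert.
- **7.2 (non-serious events).** The data to be recorded include "and the relationship to the study drug".
- **7.3.1 (timing).** "After informed consent but prior to initiation of study medications, only SAEs caused by a protocol-mandated intervention will be collected". Other serious events are recorded from the first day of study treatment.
- **7.3.2 (all serious events).** Entry in the eCRF within 24 hours, with an email to the project manager from affiliate sites.
- **7.3.3 (expedited).** The MedWatch form is needed for an event that is a serious SAR and also unexpected. The project manager "will also be responsible for informing each Affiliate site of all serious and unexpected SARs via fax as soon as possible".

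Section 2.4.2 defines SRS toxicity by time: after SRS is complete and before erlotinib is restarted. Section 6.9.4 adds CTCAE version 4 grading and no attribution rule.

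**The concern.** The protocol gives two treatments but writes its causality rules for one. If the definitions are followed literally, the component without a route to the other sites is the one delivered in several organs and at several institutions. Section 6.9.5 itself notes that erlotinib toxicity after SRS has not been studied systematically, and 6.9.1 mentions safety concerns as a reason for holding erlotinib during radiation.

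Two things are at stake. The first is prompt sharing, between sites giving the same ablation, of a serious and unexpected complication. The second is interpretation: unless each event is attributed to a component, the toxicity results for SRS (2.2.3) and for erlotinib after SRS (2.2.4) rest mainly on the date of the event.

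**Working it through.** No statistical figure is involved, so the check is to follow the definitions for three kinds of serious event and then look at the two timing rules.

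**1. Which events reach the affiliate alert?**

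| Attributed cause | SAR under 7.1.2? | Expectedness reference under 7.1.3? | Affiliate fax under 7.3.3? |
|---|---|---|---|
| Erlotinib only | Yes | Erlotinib product information | Yes, if unexpected |
| Possibly both | Yes, a drug cause is reasonably possible | Erlotinib product information | Yes, if unexpected |
| SRS, surgery or other ablation only | No | None named | No written trigger |

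Broader terms do occur in section 7. One causality factor in 7.1.2 is "known mechanism of action or side effect profile of study treatment", 7.1.1 refers to study therapy when discussing disease progression, and 7.3.1 refers to interventions required by the protocol. None of them widens the SAR definition on which 7.3.3 depends.

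**2. What still happens to the ablation-only event?** It is entered in the eCRF within 24 hours. If it occurs at an affiliate, the project manager is emailed (7.3.2). UNC personnel inform the Principal Investigator (7.3.3). It goes to the UNC IRB within 7 days if it is an Unanticipated Problem, and otherwise in the annual list; affiliates with their own IRB follow local policy. The DSMC reviews safety data quarterly to annually, and the study team meets (7.4). None of these steps requires prompt notice to the other affiliate sites.

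**3. Can timing replace attribution?** For patients already on erlotinib, 4.3 recommends a restart 3 days after SRS, allows it sooner, allows erlotinib never to be stopped, and does not allow it later.

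- Longest window when 4.3 is followed: 3 days.
- Window for a patient who never stops: none.
- SRS effects that appear after the restart: outside the window in every case.

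The post-SRS visit, where toxicity is evaluated, may fall on the last day of radiation (6.1, footnote 2). Section 6.9.1 also says that erlotinib is held during SRS, while 4.3 makes this a recommendation; the two must be reconciled, because the existence of the window depends on it.

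**4. Start of serious-event collection (7.3.1), a secondary point.** Take a patient who holds erlotinib and has a serious event during the SRS period.

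- Caused by SRS: collected, since SRS is an intervention required by the protocol.
- Not caused by SRS: excluded by the first rule, because study medication has not begun; required by the second, if SRS counts as study treatment.

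Example length, from the ten-fraction lung schedule in 4.2.2f (daily, weekends excepted): ten weekday fractions span 12 calendar days from a Monday start and 14 from any other weekday. Adding the recommended 3 days to restart gives 12 + 3 = 15 to 14 + 3 = 17 days.

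**The case against.** The strongest reply is that every serious event, whatever its cause, already leaves the reporting site quickly through 7.3.2 and 7.3.3. That stands. The gap is confined to the onward notice to other affiliates. A reader might divide planned accrual by the DSMC or IRB review interval to count patients treated before anyone outside the site knows of an SRS event. The documents do not support such a count, because those intervals do not govern when the coordinating centre learns of it.

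A reader might also infer that ablation events will be recorded as unrelated. No section says so. The relationship item stands in the section on non-serious events, 7.3.2 prescribes none for serious ones, and the eCRF itself is not among the documents. What can be said is that no attribution to ablation is required.

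Nor does it follow that SRS and erlotinib toxicity cannot be told apart. Section 2.4.2 gives a time rule and 6.3.1 a post-SRS toxicity evaluation. The rule works for early events in patients who stop erlotinib; for late events and for patients who continue it, it does not.

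Finally, 7.3.3 implements drug-reporting rules for an IND study, and SRS is given according to standard of care, so drug wording there is partly a matter of scope. That is fair for submission to the FDA. It is a weaker reason for limiting the trial's own notice between sites, given that SRS toxicity is an objective.

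**Conclusion.** The point holds in a bounded form. As written, a serious unexpected event attributed solely to SRS, surgery or other ablation is not a SAR, has no named expectedness reference, and has no written trigger for prompt notice to the other affiliate sites. An event that may be due to both treatments can still qualify.

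The rules apply to all 40 planned patients, since all are to be ablated. The number of events affected cannot be estimated, because the documents give no expected rate of serious ablation complications. Objectives 2.2.3 and 2.2.4 are partly separable: a window of at most 3 days for patients restarting erlotinib under 4.3, and none for those who continue it. The ambiguity in 7.3.1 is narrower. It concerns serious events not caused by the intervention, in patients who hold erlotinib, over about 15 to 17 days for a ten-fraction lung course.

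This rests on a literal reading of section 7 and on the assumption that no other study document, such as the eCRF or a site manual, already requires attribution to ablation or a wider notice. It should be corrected; it does not show that serious SRS events go unreported.

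**What to change.** - In section 7, define study treatment as SRS or other local ablation and/or erlotinib, and use that term in the SAR and causality definitions.
- Record relationship to ablation and to erlotinib separately, for serious and non-serious events. This gives 2.2.3 and 2.2.4 a basis beyond the time window in 2.4.2.
- Name a reference for the expectedness of SRS and other ablation effects.
- Extend the affiliate notice in 7.3.3 to serious unexpected events related to either component, leaving the FDA drug-reporting duties unchanged.
- In 7.3.1, use a single start point for collecting all serious events: the first SRS fraction or ablation procedure.

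The cost is protocol wording, one added eCRF field and a few more notices to sites. No visit, treatment or sample size changes.
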